Research shows that women often lack information about physical and mental and urogenital changes under the "middle of life" / menopause (7).

Group education is a method and participation in group education can be a good way for women to get information and exchange experiences (8).

Earlier studies evaluating patient education in hypertension and diabetes show significant improvement (9.10). Talking can raise awareness about choices and consequences, create insight into behaviours and provide insight into the overall life situation to find the core of ill health (11). Arving et al shows that health-related quality of life increased faster in patients receiving support calls than those who received normal treatment (12).

There is a lack of primary care studies that evaluate the effect of education in group and / or individually for women 45-60 years with stress-related symptoms.

The vast number of middle aged women with ill health and subsequent high risk for disease risk and increasing number of long-term sick leave shows that it is important to study women's health in this age group.

Aim

To study the effect of education in a group or individually delivered in primary health care on mental health, quality of life and sick leave in women aged 45-60 with stress-related symptoms.

Research questions

- A. Is there any effect of group information (GI) on quality of life, mental health, sick leave or visits to a primary health care centre compared to a control group?
 1. What is the effect of group education (GI) on quality of life (measured by change in scores in SF36 from baseline to 6 months after completed intervention) –
Primary research question (other questions are secondary).

Study protocol: Effect of primary care education on mental health, quality of life, need for sick leave and health care consumption in women 45-60 years with stress-related symptoms. A randomized controlled trial.

2. What is the effect of group education (GI) on quality of life (measured by change in scores in SF36 from baseline to 12 months after completed intervention)
3. What is the effect of group education (GI) on change in number of days on sick leave. (At baseline the number of days on sick leave up until present time is stated by women currently being on sick leave. At the 6 month follow the same information is retrieved is retrieved. The change is the difference between these measurements.)

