The research nurse is responsible for administration of questionnaires and arranging physical check-up.

Group allocation

Research randomizer is used to generate a random series based on block-randomization in blocks of four. The random series is transferred to closed sealed opaque envelopes, each containing group assignment. The manufacture of these closed envelopes is done by a person who is not involved in the study.

Randomization occurs after the woman answered all questionnaires at baseline. Then the research nurse opens the next sealed numbered envelope and the patch inside describes what group the woman is allocated to:

- Group 1: group information (GI)
- Group 2: group information (GI) + person-centred support (PCS)
- Group 3: person-centred support (PCS)
- Group 4: no GI or PCS (control group)

Intervention

Group information (GI).

Midwives and district nurses participate as group leaders. Each group training includes 12 women and comprises four one-and-a-half hours of information with topics related to physical and mental changes in the body as well as conversations aimed to make behaviour, consequences of behaviour and choices in life conscious.

Study protocol: Effect of primary care education on mental health, quality of life, need for sick leave and health care consumption in women 45-60 years with stress-related symptoms. A randomized controlled trial.

The first group event contains education with the definition and myths of "middle of life" / menopause, physiology, menstrual cycle, hormonal conversion, local oestrogen deficiency symptoms, osteoporosis and information on treatment options and self-care advice.

The second group event contains teaching and information on cardiovascular health, its risk and health factors, physiology, mental health, relationships, sexuality and lust as well as information on treatment options and self-care advice.

The third group event contains insights into stress-related ill health, physiology, social relationships in family and work, sexuality and lust, insight into obstacles and resources, coping strategies and behavioural changes to promote health.

The fourth group event contains insights on relationships, sexuality and lust as well as a summary of "How do we want to live to feel good?" Insight into obstacles and resources, coping strategies and behavioural changes to promote health.

Structured person-centred support (PCS):

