Individually structured person-centred education is carried out by a district nurse or midwife. It includes five sessions. The conversation contains dialogue on symptoms of stress-related ill health, what is happening in the body (physiology), relationships, coping strategies, requirements, guilt, exercise and diet. Women randomized to receive both group education and individual education will receive group education first.

Control

The research nurse informs women in all groups that they can contact the primary health care centre if they wish to explore what can be offered from there. If the woman contacts the health care centre, they are treated according to the health care centre's current routines. Hence, any education or treatment provided outside the scope of this research project can vary between health care centres. Group education and individual education for the other groups are provided on top of the primary health care centre's standard measures.

Data collection

The following information is collected at baseline.

- Demographic data: age, work, education, family situation, hormone treatment, cardiovascular disease, stress disorder, cause of healthcare contact (psychological and / or physical) and prior sick leave days. In addition, they are asked if they have visited the healthcare centre for the past two months as a patient and, if so, for what (a number of standard symptoms can be selected)
- Blood pressure: blood pressure with electronic blood pressure cuff, if necessary manual blood pressure, the mean of two blood pressure is recorded at the time of visitation.
- MRS: measures the occurrence of menopausal symptoms. The questionnaire consisting of 11 questions brings together menopause symptoms in three main groups; somatic symptoms, urogenital symptoms and mental symptoms. The questionnaire

Study protocol: Effect of primary care education on mental health, quality of life, need for sick leave and health care consumption in women 45-60 years with stress-related symptoms. A randomized controlled trial.

indicates the severity of symptoms on a 5-degree scale. Low incidence of symptoms indicates 0 points and high incidence of symptoms 4 points. Total sum, individual questions and three subgroups are reported. The instrument has been tested for reliability and validity (14).

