- MADRS: investigates the degree of depression and depressive symptoms. The questionnaire consists of 9 questions, which are graded on a 6-degree scale where 0 points indicate a low incidence of symptoms and 6 points indicate a high incidence of symptoms and ill health. The instrument has been tested for reliability and validity (15).
- SF-36: examines physical and mental health as well as changes over time. The questionnaire consists of 36 multiple-choice questions, divided into eight subdivisions. Scores are between 0 - 100, higher value indicates better health experience. The instrument has been tested for reliability and validity (16).
- HAD: investigates the degree of anxiety and depressive symptoms. The form consists of 14 questions with seven issues that measure anxiety (HAD-A) and seven issues that measure depression (HAD-D) and graded on a 4-degree scale. Each question can yield between 0 and 3 points and summed to give a score scale of 0-21 for respective anxiety and depressive symptoms. Higher points indicate higher incidence of symptoms. The instrument has been tested for reliability and validity (17).
- s-UMS, self-assessed fatigue syndrome. Identify individuals who have developed or may be developing a clinical fatigue syndrome with impaired work ability and increased risk of sick leave. The form has four questions with queries. The instrument has been tested for reliability and validity (18).
- PSS-14: Measurement of self-assessed general perceived stress. how often you have experienced life as unpredictable, uncontrollable and congestive in the last month. The form has fourteen questions. The Swedish translation has shown good internal validity (19).
- AUDIT: self-assessment test for alcohol consumption and consists of ten questions divided into three domains: consumption, addiction and alcohol-related injuries. Results above the cut-off limit 6 points for women and 8 points for men indicate a risky drinking. The instrument has been tested for reliability and validity (20).

Follow-up of intervention takes place six and twelve months after completion of treatment / education. Midwife and district nurse participate in the follow-up. During this visit, follow-up of quality of life, mental health, care needs and sick leave is made by the woman filling in the same questionnaire as at baseline.

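### Follow-up is timed from completion of the intervention, so the control group has no defined visit date and the combined arm is assessed later after baseline than the group-education arm.

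*Combined protocol and SAP*

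**What the plan says.** The primary research question (A.1) measures "change in scores in SF36 from baseline to 6 months after completed intervention". The Data collection section applies the same rule to every follow-up: "Follow-up of intervention takes place six and twelve months after completion of treatment / education". A later paragraph of that section repeats it for data collected by the research nurse, with no separate rule for controls. Some secondary questions (sick leave, health-centre visits) refer only to 6 or 12 months and do not say from when.

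Under Group allocation, "Randomization occurs after the woman answered all questionnaires at baseline", so baseline comes before allocation in every arm. Group 1 receives GI, Group 2 GI and PCS, Group 3 PCS, and Group 4 neither.

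Under Intervention, "Each group training includes 12 women and comprises four one-and-a-half hours of information". Of PCS the protocol says "It includes five sessions", and Group 2 has GI before PCS. Session spacing, start delay and visit windows are not given.

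The Statistical analysis section fits GI, PCS, their interaction and age. It does not state the coding of the two factors and has no term for time since baseline.

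**The concern.** The stated rule cannot be applied to the comparator in the primary question. Group 4 completes nothing, so someone would have to choose its visit dates during the trial, knowing the allocation.

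In the arms where the rule can be applied, it ties time since baseline to the allocation. Group 2 must finish two courses in sequence before its clock starts, while Group 1 finishes one. Symptoms, sick leave and quality of life can change over time without treatment, and where they do, the difference in elapsed time is mixed with the treatment contrasts.

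The sick-leave outcome depends on the visit date in a further way. The protocol says "At baseline the number of days on sick leave up until present time is stated by women currently being on sick leave" and asks for the same information at follow-up. Continuing spells lengthen with a later visit and ended spells drop out, so the net direction is unknown.

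**Working it through.** **The plan's own figure.** The sample size for the primary question reproduces. With d = 3/8 = 0.375, two-sided 5% and 80% power, a t-test needs 112.6 per group. Dividing by the Mann-Whitney efficiency 3/π gives 117.9, rounded up to 118, or 236 in total, as stated. The timing rule does not enter this calculation, so 236 is unaffected.

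**Inputs from the protocol.** Four GI sessions; five PCS sessions; GI before PCS in Group 2; SD 8; target difference 3 points; 370 women (185 per factor level, 92.5 per arm).

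**Assumptions, not in the protocol.** First session at randomisation; equal spacing of *s* weeks, 1 to 4, for both interventions; one interval between GI and PCS in Group 2; linear SF-36 drift of 0.2 points per month in either direction; 4.35 weeks per month. Controls are given a reference date *c* weeks after randomisation.

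**Weeks from randomisation to the start of the follow-up clock**

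- Group 1: 3s
- Group 3: 4s
- Group 2: 3s + s + 4s = 8s
- Group 4: c (undefined in the protocol)

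Group 2 minus Group 1 is 5s = 5–20 weeks. Group 2 minus Group 3 is 4s = 4–16 weeks. Neither depends on c. If GI starts after a wait of w weeks and PCS in Group 3 after v weeks, the first difference stays 5s and the second becomes 4s + w − v. Group 2 is therefore later than Group 3 unless v exceeds w + 4s. The first result takes the average wait for GI to be the same in Groups 1 and 2, as randomisation to the same programme implies.

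**Extra elapsed time in each contrast**

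| Contrast | Formula | c = 0 | c = 3s (GI completion date) |
|---|---|---|---|
| GI, averaged over PCS | [(3s − c) + (8s − 4s)]/2 | 3.5–14 wk | 2–8 wk |
| GI, 0/1 coding (Group 1 v 4) | 3s − c | 3–12 wk | 0 |
| PCS, averaged over GI | [(4s − c) + (8s − 3s)]/2 | 4.5–18 wk | 3–12 wk |
| Interaction | 8s − 3s − 4s + c | 1–4 wk | 4–16 wk |

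A wait of w weeks to fill a GI group of 12 adds w to both GI contrasts at c = 0.

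**Bias and type I error**

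Bias = weeks/4.35 × 0.2. Type I error = P(|Z + bias/SE| > 1.96).

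Standard errors:

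- averaged effect: 8 × √(2/185) = 0.83
- Group 1 v Group 4: 8 × √(2/92.5) = 1.18
- interaction: 8 × √(4/92.5) = 1.66

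| Contrast | Bias (points) | Type I error |
|---|---|---|
| GI averaged, c = 0 | 0.16–0.64 | 5.4–12.1% |
| GI 0/1, c = 0 | 0.14–0.55 | 5.2–7.6% |
| PCS averaged, c = 0 | 0.21–0.83 | 5.7–16.9% |
| Interaction, c = 3s | 0.18–0.74 | 5.1–7.3% |

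At 0.1 points per month the biases halve, and the largest GI type I errors are 6.7% (averaged) and 5.6% (0/1). At zero drift the bias is zero. With no gap between GI and PCS, averaged GI at c = 0 has 3–12 weeks of extra time, a bias of 0.14–0.55 points and type I error of 5.3–10.2%.

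No sick-leave figure is given, because spell durations are not in the documents.

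**The case against.** Timing from completion is a legitimate choice if the aim is to measure how long an effect lasts. It equalises time since the last session, and Group 2's later visit is the price. Timing from randomisation removes one imbalance and creates another: at 1–4 week spacing, time since the last session would differ by 5–20 weeks between GI and the combined arm. Nothing in the documents shows that drift is worse than decay of effect. This stands as a trade-off that the protocol should state and justify. It does not supply a date for Group 4.

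The harm also rests on assumed quantities. The plan assumes zero SF-36 change in controls, which gives zero bias. A drift of 0.2 points per month is 1.2 points over six months, 40% of the 3-point target. The 12% figure needs that drift, 4-week spacing, controls timed from randomisation and averaged coding all at once. In the illustrated schedules every first follow-up falls at least six months after randomisation, so only drift after that matters, and early regression to the mean may be over. These points limit the likely size and stand. However, the plan does not treat controls as static on every outcome. Its sample size section assumes a 0.5-day fall in sick leave among controls, and cites a pilot in which control MADRS scores rose by 0.10.

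Finally, completion in Group 2 could be read as completion of GI alone. That would remove the lag behind Group 1, but Group 4 would stay undefined, and the PCS questions would need a different starting point for the same visits.

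**Conclusion.** The concern holds and should be fixed. Two parts follow from the text alone: Group 4 has no defined follow-up date for the primary comparison, and Group 2 is assessed later after baseline than Group 1 whatever date controls are given. The second part reads completion in Group 2 as completion of both courses. The lag behind Group 3 is conditional on start delays.

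The effect on results cannot be sized or signed from the documents, because spacing, delay and drift are not stated. Which contrast is affected also depends on the control date and the coding. The question asks about GI "visits to a primary health care centre compared to a control group", which matches 0/1 coding, but the model's coding is not given.

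The figures are illustrations, not bounds. On those assumptions the GI and interaction biases stay below one standard error and below a quarter of the 3-point target (0.75). The averaged PCS bias reaches 0.83 points, about one standard error. This does not invalidate the trial, but it affects the primary endpoint and cannot be repaired once the visits have taken place.

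**What to change.** Time both follow-ups from the date of randomisation, with the same schedule and visit window in all four groups, late enough for the combined arm to have finished. Record completion dates, report time from baseline to each visit by arm, and add a supplementary analysis by time since completion.

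The cost is a protocol amendment, with no extra visits. The SF-36, MADRS, PSS-14 and HAD questions must be reworded to refer to time after randomisation. The question moves from durability after completion to effect at a fixed time, and time since the last session will then differ between arms.

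If the completion rule is kept, at minimum define a reference date for Group 4 in advance and report elapsed time by arm. This leaves Group 2's later visits unresolved. Giving controls the GI completion date removes the extra time from the 0/1 GI contrast but raises the interaction's imbalance from one session interval to four.

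Do not adjust for elapsed time as a covariate: it arises after randomisation and is largely fixed by arm.

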23. What is the effect of Structured person-centered support (PCS) on visits to primary health care (women are asked at baseline if they had to visit the primary health care center during the preceding two months. The same question is asked at 6 months. The measurement is the change in proportion of women who visited the primary health care center)?
24. What is the effect of Structured person-centered support (PCS) on visits to primary health care (women are asked at baseline if they had to visit the primary health care center during the preceding two months. The same question is asked at 12 months. The measurement is the change in proportion of women who visited the primary health care center)?

Methods

Selection of patients, inclusion criteria and logistics

Women, 45-60 years old, reached through advertisements in newspapers and on a website, are offered to participate in the study. Application for participation in the study is made electronically via Fou Primary Care Södra Älvborg website or by telephone to research nurse. Inclusion criteria:

Study protocol: Effect of primary care education on mental health, quality of life, need for sick leave and health care consumption in women 45-60 years with stress-related symptoms. A randomized controlled trial.

- a. The woman has some mental and / or physical health problems such as depression, anxiety, gastrointestinal symptoms, muscular symptoms and / or cardiovascular symptoms.
- b. The woman has been on sick leave for a maximum of 30 days in the last two months.
- c. The woman has no major language difficulties that prevent understanding and speaking Swedish language as well as filling in forms.
- d. Woman lacks serious illness such as psychosis, severe depression or dementia
- e. The woman is not treated in palliative care
- f. The woman has no ongoing drug or alcohol abuse.

Research nurse contacts the woman via telephone and provides further information about the study where the opportunity is given to ask questions. If the woman meets all inclusion criteria and choose to accept the study, electronically self-administered questionnaires about self-assessed health and health-related quality of life will be sent to all participants, as well as a written informed consent that is signed. Self-administered questionnaires and consent kits are filled in via link on R & D Primary Care Södra Älvborg's website.

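### Outcome questionnaires are filled in at a visit attended by a midwife and district nurse, the professions that give both interventions, and nothing keeps a woman's own educators away from her answers

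*Combined protocol and SAP*

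**What the plan says.** At baseline, the section on selection of patients, inclusion criteria and logistics states: "Self-administered questionnaires and consent kits are filled in via link". Under Group allocation, the envelope is opened only after these forms are answered, so baseline answers cannot depend on arm.

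For follow-up, the Data collection section says: "Follow-up of intervention takes place six and twelve months after completion of treatment / education". It continues with "Midwife and district nurse participate in the follow-up", and then: "During this visit, follow-up of quality of life, mental health, care needs and sick leave is made by the woman filling in the same questionnaire". Completion of the outcome forms is thus placed inside the visit.

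Under Intervention, the GI text says "Midwives and district nurses participate as group leaders" and the PCS text says "Individually structured person-centred education is carried out by a district nurse or midwife". Group 4 receives neither.

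The research nurse also has a part. That nurse administers the questionnaires and collects the data at baseline and at both follow-ups (Selection and Data collection sections). Under Group allocation, the research nurse also opens the envelope and so learns the arm.

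The documents do not say that follow-up staff are blinded, that they are different people from those who taught the woman, or that she answers out of their sight. They also do not say whether the follow-up forms are electronic.

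**The concern.** All 24 research questions rest on what the woman reports: SF-36, MADRS, PSS-14, HAD, her stated days of sick leave, and whether she visited the health care centre. None has an independent source that could serve as a check. Women cannot be blinded to education, so the way outcomes are collected is one of the few protections left.

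A woman in an educated arm has had four group sessions, five individual sessions or both, on subjects such as stress, relationships and coping. If those who taught her are present at follow-up, she may report more improvement than she would in private. A control woman has no such tie from the trial. A difference of this kind favours education, and the regression cannot separate it from a treatment effect.

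**Working it through.** **1. The plan's own figure.** For question 1 the Sample size estimation section assumes a gain of 3 points against 0, SD 8, two-sided 0.05 and power 0.80, with the Mann-Whitney test. The effect size is 3/8 = 0.375. A two-sample t-test needs 112.6 women per group. Multiplying by π/3 for the Mann-Whitney test gives 117.9, rounded up to 118 per group, or 236 in total, as stated. SD 8 and the planned total of 370 are used below. The sample size is not in dispute.

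**2. Assumptions.** The documents give no size for a reporting shift. I take b = 0.5, 1 and 1.5 SF-36 points, which is one sixth to one half of the planned 3-point effect. I also assume no true effect, four equal arms of 370/4 = 92.5, no drop-out, a normal approximation and no allowance for age adjustment.

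**3. Formula.** With a shift δ in a contrast that has standard error SE, the chance of a significant two-sided result is Φ(δ/SE − 1.96) + Φ(−δ/SE − 1.96).

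**4. Which contrast, and how much of the shift reaches it.** The Statistical analysis section enters GI and PCS as two factors and evaluates their interaction. It does not say how the factors are coded, so the GI effect can be read in two ways.

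- GI main effect, groups 1+2 against 3+4: SE = 8 × √(4/370) = 0.832. Group 3 receives PCS from the same professions. If every educated arm shifts by b, the GI side shifts by b and the non-GI side by (b + 0)/2. The contrast therefore shifts by δ = b/2.
- GI only against control, group 1 against group 4: SE = 8 × √(2/92.5) = 1.176, and δ = b.

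For comparison, if the shift falls on GI women alone, the main-effect contrast carries all of it: δ = b with SE 0.832.

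**5. Results: false-positive rate (nominal 5%).**

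| Shift b (points) | Every educated arm, GI main effect (δ = b/2, SE 0.832) | GI only against control (δ = b, SE 1.176) | GI women alone, GI main effect (δ = b, SE 0.832) |
|---|---|---|---|
| 0.5 | 6.0% | 7.1% | 9.2% |
| 1 | 9.2% | 13.6% | 22.5% |
| 1.5 | 14.7% | 24.7% | 43.8% |

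One cell in full: for b = 1 in every educated arm, δ/SE = 0.5/0.832 = 0.601, and Φ(−1.359) + Φ(−2.561) = 0.087 + 0.005 = 0.092.

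**6. Change of mode.** If follow-up is on paper or in person after a web baseline, this applies to all four arms. A common shift m adds m to each arm mean, and m − m = 0 in any contrast between arms. It would distort change within an arm but would largely cancel in the comparison.

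**The case against.** The strongest reply is that the plan names one role, the research nurse, for questionnaires at all three time points and gives that role no teaching. The text on follow-up names professions, not persons. It does not say that the attending midwife and district nurse taught this woman, or that they watch or handle her forms. The mention of returned questionnaires also fits forms that are handed or sent in. On this view, the gap is only a missing detail about who attends.

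Part of this stands. A reader might infer that women answer in front of their own teachers; the documents do not say so. A reader might also infer that moving from web to visit itself favours education. The follow-up format is not stated, and a change common to all arms would largely cancel.

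The rest does not remove the point. Naming the research nurse does not take the other two professions out of the visit, and that nurse knows the allocation. Completion during the visit is a stated procedure, and no sentence separates a woman's educators from it.

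It is also fair to say that the fix is partial. Unblinded women can still report favourably through a web form, and the answers come six and twelve months after the sessions end. The visit setting is the avoidable part.

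**Conclusion.** The concern holds as an avoidable risk of bias in favour of education. It is not a demonstrated bias. It rests on three things in the text: completion during the visit, attendance by the professions that teach, and the lack of any safeguard that separates a woman's educators from her answers. Whether the attending staff are her educators is open.

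The size is unknown. If every educated arm shifts by 0.5 to 1.5 points, the false-positive rate for question 1 is about 6% to 15% for the GI main effect and about 7% to 25% for GI only against control, under the assumptions listed in the working. A reader might infer the larger figures of 9%, 22% and 44%. Those need the GI and non-GI halves to differ by the full shift, as when it falls on GI women alone. The documents do not support that as the main case, because PCS is given by the same professions and half of the non-GI comparator receives it.

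This is a worthwhile, low-cost improvement to data collection. It does not affect the sample size or the interventions.

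**What to change.** In the Data collection section, state that women in all four arms complete the 6- and 12-month questionnaires through the same web link as at baseline, before the follow-up visit. Add that staff who led a woman's group or gave her PCS neither assist with the forms nor see her answers. The visit can stay for other purposes.

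The cost is a sentence or two, since the link already exists, plus reminders before the visit. Some women may still answer at the visit. Record these forms as such, so that their number can be reported by arm.
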